Hypothesis 2.2: Cartilage defects at or near the chondrolabral junction are prognostic indicators of worse outcomes as determined by the mHHS.

Hypothesis 2.3: Subjects with any degree of joint space narrowing (classified by Tonnis and Kellgren-Lawrence grading, see below) on plain radiographs will have more pain, regain less function, and do more poorly based on validated outcome measures, specifically the mHHS, at 6 and 12 months than subjects without any degree of joint space narrowing on plain radiographs.

EXPLORATORY Specific Aim 3: To evaluate the relationship between joint space narrowing on plain radiography and arthroscopically proven osteoarthritis.

Hypothesis 3.1: Tonnis grading and Kellgren-Lawrence grading on plain radiography are not predictive of the severity of arthritis at the time of arthroscopy.

Specific Aim 4: To analyze the data of subjects crossing over from PT alone to PT and surgery.

Hypothesis 4.1: Primary outcome scoring (mHHS) at 12 and 24 months after cross to surgery and PT will differ significantly from those initially randomized to surgical treatment.

Hypothesis 4.2: Baseline scores on outcome measures of those subjects crossing over will not differ significantly from those obtained at the time of crossover.

III. SUBJECT SELECTION & ENROLLMENT:

Study Overview: This is a prospective randomized control trial (RCT), which will enroll subjects with a clinically diagnosed tear of the acetabular labrum. Subjects who have been diagnosed with a labral tear in clinic will receive conservative physical therapy treatment alone or arthroscopic surgical labral repair and physical therapy. If it is discovered that there is unexpected pathology at the time of arthroscopy for subjects in the surgery group, those subjects will be removed from the study. This is due to the possibility that the source of pain is less likely a result of the dysfunction of the labrum and more likely due to aberrant extra-articular biology. We will use validated outcomes measures that include the mHHS, LEFS, HOS, NAHS, and iHOT-33 (see below) and review the medical record for physical exam findings to track patient progress throughout their involvement in the study which will continue for as long as they are a patient of the PI. Study procedures will be complete when the last enrolled subject completes 24-month follow-up and completes the corresponding surveys.

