Patient Satisfaction: This questionnaire will be disseminated to subjects yearly starting around the time of their 1-year follow up clinic visit and yearly thereafter. The questionnaire will contain 3 items. The purpose is to gauge how satisfied with each subject is with 1) their specific treatment regimen during the study 2) their outcomes of their specific therapy and 3) if given the choice, would the subject undergo the same therapeutic regimen. (See addendum)

Participation questionnaire: This 6-item questionnaire was designed to assess how patients felt about their care during the study, if they would participate in a similar study, how well they feel the outcomes measures addressed their hip condition, and what factors, if any, would increase participation in a future study. (See addendum)

Study compliance monitoring, treatment credibility assessment, and data management:

Subjects will be given contact information for the IRB and study coordinator. Subjects will also be seen in clinic. In addition to regular clinical follow-up the purpose of these interactions is to identify adverse events, patient concerns, and to check on patient compliance with physical therapy regimen, which is particularly important over the first 3 months. At the end of the trial all subjects will complete an

exit questionnaire. All data is collected with RedCap electronic software, which reports on missing data and data outliers. We can also then quantify and analyze treatment compliance.

PHYSICAL THERAPY VISITS

Please see attachments for post-operative and non-operative physical therapy protocols as well as advancement criteria.

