In addition, subjects can subjectively withdraw from PT any time point if they feel that it is not working for them the way they would like. However, in order to standardize the amount of time that lapses between enrollment and potential cross-over, subjects wishing to transition to surgical treatment cannot do so until 6 weeks after initial enrollment (see figure 5 of the study schema). There are several reasons for this: First, we want subjects to have enough time to see the benefits of PT, as they may not be immediate. Second, if the decision to cross over is made prior to 6 weeks, the remaining time allows for scheduling of a follow-up appointment in a timely manner that does not delay appropriate patient care. Lastly, subjects are not required to continue under the PT protocol, they can stop at any point and not receive further PT or medically directed care until their follow-up. This scenario is no different than if a patient, in a non-study setting, self discontinued a recommended course of PT and sought surgical consultation elsewhere. The advantage here is that subjects will already be known to both the hospital system and surgeon, which allows for quicker consultation.

SURGERY

While randomization is a research procedure for this study, the surgery itself is not a research procedure. This surgery is standard of care for patients with symptomatic labral tears, and the PI regularly performs labral repair in patients not enrolled in research.

POSTOPERATIVE PROTOCOL

All procedures are performed on an outpatient basis. Patients are allowed flat-foot full weight bearing immediately postoperatively. Patients are instructed in gait training, keeping a level pelvis and avoiding any lurching of their pelvis during ambulation. Patients are kept weight bearing as tolerated with crutches for 6 weeks postoperatively for a labral repair. Patients are allowed full active range of motion as tolerated immediately with avoidance of deep squatting and impact loading exercises for 4 months postoperatively. This is considered standard practice.

V. BIOSTATISTICAL ANALYSIS

Hypothesis 1.1-1.4:

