We plan to track the effects of OA on outcomes through identification and localization of OA at the time of arthroscopy using a mapping technique (see diagram). After complete visualization of the intra-articular space, as is standard practice in hip arthroscopy, classification of any existing osteoarthritis will be done according to the Outerbridge grading scale. Using this system, we are able to categorically group subjects based on location and severity of disease. If multiple lesions are present, subjects will be characterized by the most severe grade. Furthermore, based on the data gathered through meeting hypotheses 1.1-1.4, we will subdivide primary outcome scores into four categories.⁶⁰ Category I, excellent outcomes (mHHS ≥ 90); Category II, good outcomes (mHHS ≥ 80); Category III, fair outcomes (mHHS ≥ 70), and Category IV, poor outcomes (mHHS < 70). The likelihood of outcomes based on Outerbridge grading and outcome category will be determined through odds ratios. Analysis will be carried out using Chi-squared tests. Significance is set at $P < 0.05$. Linear regression analysis will be performed to detect if any relationship exists between the severity of osteoarthritis and short-term outcome scoring.

Hypothesis 3.1:

This is an exploratory hypothesis whose assessment will no influence the other data sets. Prior work by other groups has demonstrated that evaluation of arthritic burden by conventional measures (Kellgren-Lawrence and Tonnis grading) are not indicative of the severity of arthritis found at the time of arthroscopy.⁵⁸ We will explore this phenomenon in our own cohort of subjects, specifically those in the surgical group and report our findings. We will correlate our findings for significance.

Power Analysis:

Specific Aim 1, Hypotheses 1.1-1.4: *To evaluate if physical therapy alone or arthroscopic labral repair and physical therapy is of greater benefit to patients presenting at age 40 with tears of the acetabular labrum.*

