Using the data from our retrospective review of outcomes following labral repair, a 10 point or greater difference on the mHHS as significant, and a single-tail independent t-test to evaluate the difference between means with 80% power and a 5% significance level, 35 subjects are needed to demonstrate a statistically significant difference between the average mHHS of the conservative group and surgical group. Testing of hypothesis 1.5 will be an intragroup analysis looking for a significant difference in outcome measures from the time of completion of PT (non-crossover) when compared to the same data to be collected at 12 months and 24 months. The purpose is to determine the short-term durability of the response to PT, if one is found.

70 study completers should provide us with the necessary data needed to substantiate or reject our hypothesis. There has been no prospective trial to date testing these hypotheses in the hip, but we expected a 7.3-10.3% dropout rate based on the results of a similar study in the knee. However, as of July 2018, we had 47 patients that had passed the 2-year follow-up mark, of which 5 patients were no longer in the study (combination of lost to follow-up and proceeding to total hip arthroplasty), and another 11 had yet to complete their 2-year surveys even with multiple attempts to contact them and encourage them to do so. With a yield of 31 patients out of 47, or 65.95%, we increased our sample size to 122.

Therefore, we estimate needing 122 subjects to achieve 70 study completers, in the appropriate proportion of 35 subjects per treatment arm. We enroll until reaching at least 35 subjects in each group.

The results of the MeTeOR trial in the knee show that we can expect a higher drop-out rate in the surgical group. As such, this cohort may be our limiting factor.^{40, 43, 61, 62}

Specific Aim 2. Hypotheses 2.1-2.3: *To evaluate the significance of arthritic burden on short term outcomes following arthroscopic labral repair.*

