Hypothesis 2.1 was powered on the basis of our prior work where 33% of study participants had grade 4 Outerbridge changes the time of arthroscopy. Dividing our cohort into two subgroups: 1) Those with grade 4 changes and 2) Those without. We will need 12 subjects with grade 4 changes in order to perform adequate sub-group analysis.⁶³ Powered to 80% and 5% significance level. Hypothesis 2.2 is another sub-group analysis that will be conducted in a similar fashion to that of hypothesis 2.1. However, the two groups will be categorized into: 1) cartilage defects at or near the chondro-labral junction and 2) cartilage defects not at or near the chondro-labral junction. We cannot control the heterogeneity of the subjects enrolled, but based on this analysis we expect to meet our target enrollment. Hypothesis 2.3 will be analyzed via linear regression and is appropriately powered.

Specific Aim 3 is exploratory. Since we are recruiting subjects for the main purposes of determining outcomes, we recognize that we may be underpowered for the definitive analyses of our radiographic correlation hypotheses. Nevertheless, we anticipate that we will enroll sufficient numbers of subjects to draw an association or at the very least, trend patient outcomes with degree of joint space narrowing, Kellgren-Lawrence grading, and Tonnis grading. There should also be sufficient numbers to preliminarily assess any correlations between pre-operative Kellgren-Lawrence and Tonnis grades with the Outerbridge classification at the time of arthroscopy.

VI. RISKS & DISCOMFORTS

Conservative Treatment: Subjects can expect the routine discomfort associated with any therapeutic procedure. Complications may include muscle soreness, pain, and increased edema or muscle fatigue.

Operative treatment: Since surgery is not considered a research procedure (only the randomization into the surgery group is considered a research procedure, as explained above) surgical risks are explained in the surgical consent process.

In the rehabilitation period, patients will be subject to the same potentials discomforts as those subjects in the conservative treatment group as the physical therapy protocols for both groups are identical. In both treatment groups every effort will be made to minimize the risk of adverse events and patient discomfort.

VII. POTENTIAL BENEFITS:

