1. The study staff will meet regularly with [name] to review study participants and the data that has been collected on them to date. If a subject becomes disqualified or must leave the study for safety concerns, [name] will personally inform them of the situation through the subjects preferred method of contact. [name] will be leading and administering the conservative arm of the study (subjects being treated non-surgically with physical therapy and subjects in the post-operative period receiving rehabilitative physical therapy). She will inform [name] of patient progress and any potential clinically significant events that may warrant further discussion and could ultimately result in the dismissal of a patient from the study.
 - a. As this is a prospective study comparing the gold standard of treatment (labral repair) to a potentially equivalent therapeutic modality, qualifying subjects will never be denied the option to undergo labral repair via hip arthroscopy. The treatment schema allows for subjects in the non-surgical arm (physical therapy alone) to cross over to the surgical treatment group at any time (following physical therapy) from initial enrollment if they wish to do so. Subjects who decide to crossover or are indicated to crossover through the non achievement of advancement criteria will have the PT discontinued at that time point but must wait for official crossover at 6 weeks after initial enrollment. Participants can always decide to leave the study if this is not what they want. The decision to cross over will in no way affect the quality of healthcare current or prior study participants receive. All of this will also be explained to them during the consent.
 - b. We will review all data continuously and should there be a obvious clinical detriment to specific treatment arm such as repeated poor outcomes or worsening function, further investigation will be initiated to determine if this is an isolated occurrence or if there is a significant trend which warrants cessation of study protocol and disenrollment of subjects.
 - i. Stopping rules include a clear difference in morbidity, as measured by interval physical exams and outcomes questionnaires, between treatment groups
 - ii. Any significant mortality possibly linked to study procedures will result in immediate suspension of the study protocol.

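### Hypothesis 4.2 treats a non-significant change before crossover as support for no change, with no Aim 4 analysis behind it, so a small crossover group could support it wrongly

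*Combined protocol and SAP*

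**What the plan says.** Section II, Specific Aim 4, concerns subjects who move from physical therapy (PT) alone to surgery plus PT. Hypothesis 4.2 reads: "Baseline scores on outcome measures of those subjects crossing over will not differ significantly from those obtained at the time of crossover". Aim 4 is not labelled exploratory, whereas Aim 3 is.

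Section V, Biostatistical Analysis, gives analysis text for Hypotheses 1.1-1.4, 2.1-2.3 and 3.1. Its Power Analysis covers Aims 1 and 2, describes Hypothesis 1.5, and ends with Aim 3 ("Specific Aim 3 is exploratory"). Neither 4.1 nor 4.2 appears.

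Two other hypotheses also predict no difference or no association, and both are handled by significance:
- For 1.5: "Testing of hypothesis 1.5 will be an intragroup analysis looking for a significant difference in outcome measures".
- For 3.1: "We will correlate our findings for significance".

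The only mHHS difference that the plan treats as important is in the Aim 1 power text: "a 10 point or greater difference on the mHHS as significant".

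On timing, Section IV (Physical Therapy Visits) says that "subjects wishing to transition to surgical treatment cannot do so until 6 weeks after initial enrollment". Section VIII, item 1a, adds that subjects who decide to cross over, or who fail the advancement criteria, "will have the PT discontinued at that time point but must wait for official crossover at 6 weeks after initial enrollment".

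**The concern.** Non-significance depends on precision as well as on the size of the change. The fewer subjects cross over, the easier it is for 4.2 to come out as predicted, whatever happened to their scores. With the hypothesis as its own criterion and no analysis text to qualify it, sparse data would count in its favour.

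At stake is how the crossover results are read. A report that scores had not changed by the time of crossover could rest on nothing more than a wide interval. These subjects are self-selected or re-referred for inadequate response, so the finding would attract clinical interpretation.

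**Working it through.** **Inputs from the documents.** Aim 1: 10 mHHS points, one-sided 5%, 80% power, 35 per arm. Enrolment: 122.

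**Inputs that are assumptions.** The documents give none of these:
- mHHS SD, back-solved below.
- Baseline-to-crossover correlation r: 0.5, range 0.3 to 0.7.
- Two-sided 5% paired t-test for 4.2. A paired t-test is the plan's within-group method for Aim 1.
- Crossovers: 6, 12, 18, 24 or 30. These are about 10% to 50% of 61, taking 122 / 2 as the PT arm.

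**Step 1, implied SD.** The plan's 35 per arm cannot be reproduced because no SD is stated, so it is solved for. The normal approximation gives SD = 10 × √(35/2) / (1.645 + 0.842) = 16.8. The t-based solution is a standardised difference of 0.600, so SD = 10 / 0.600 = 16.7.

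**Step 2, SD of the paired change.** SD × √(2(1 − r)) gives 19.8 (r = 0.3), 16.7 (r = 0.5) and 12.9 (r = 0.7).

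**Step 3, chance of non-significance when the true mean change is 10 points.** Take 12 crossovers and r = 0.5. The standard error is 16.7 / √12 = 4.82 and the noncentrality is 10 / 4.82 = 2.07. The critical t on 11 df is 2.201. From the noncentral t, the chance of non-significance is 53%. The expected 95% CI half-width is about 2.201 × 4.82 = 10.6 points, so a null result could not reliably exclude a 10-point change.

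| Crossovers | r = 0.3 | r = 0.5 | r = 0.7 |
|---|---|---|---|
| 6 | 83% | 78% | 66% |
| 12 | 64% | 53% | 32% |
| 18 | 47% | 33% | 13% |
| 24 | 34% | 20% | 5% |
| 30 | 24% | 11% | 2% |

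The figure stays above 50% up to about 16, 12 and 8 crossovers respectively.

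**Step 4, sensitivity.**
- SD of 13 or 20 (r = 0.5, 12 crossovers): 32% or 65%.
- True change of 5 points (r = 0.5): 84% at 12 crossovers and 71% at 24.
- True change of 15 points (r = 0.5): 57% at 6 crossovers and 19% at 12.

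**Step 5, several measures.** 4.2 refers to outcome measures in the plural. Suppose six measures must all be non-significant, each with a standardised change of 0.6 and inter-measure correlation of 0.6 to 0.8 (assumed). By simulation, false support falls to 43-54% with 6 crossovers, 25-35% with 10, 18-28% with 12 and 7-14% with 18.

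**Step 6, an interval rule instead.** Require the 95% CI for the mHHS change to lie within ±10 points (r = 0.5, simulation). With a true 10-point change, the rule says no important change at most 2.5% of the time. With no true change, it reaches that conclusion about 2% of the time at 6 crossovers, 11% at 12, 35% at 18 and 60% at 24. About 32 crossovers are needed for 80% (20 to 43 for r = 0.7 to 0.3).

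**The case against.** The strongest reply is that few crossovers is a premise, since the plan gives no crossover rate. A reader might infer that 4.2 would probably be supported whatever the truth. The documents do not support that. At r = 0.5, 12 crossovers is close to a coin toss, and from 18 upwards a 10-point change would more often be detected than missed. If all measures must be non-significant, false support is below half at nearly every count examined. This part stands and limits the point to small groups.

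Second, no text says that a non-significant result will be reported as equivalence. That is true. But the hypothesis supplies no other criterion, and 1.5 and 3.1 show the same reliance on significance.

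Third, a reader might infer that variable PT exposure invalidates 4.2, because PT stops at the decision while crossover waits until at least week 6. That goes too far: 4.2 compares scores at two times and makes no claim about PT dose. The plan also foresees compliance data ("We can also then quantify and analyze treatment compliance"), though it does not link them to Aim 4.

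Fourth, margins are contestable. The 10-point figure comes from a between-arm comparison. The LEFS value in Section IV is a detectable change and the HOS values are meaningful increases. None of them is stated as an equivalence margin, and this stands as a limit on the remedy.

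The study schema figure and PT attachments are not available here and may hold operational detail on crossover. They would not normally hold the analysis, and the power text runs directly from Aim 3 into Section VI.

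**Conclusion.** The concern holds in limited form. As written, 4.2 counts failure to find a difference as support for no change, and Section V offers no Aim 4 analysis to prevent that. On the mHHS alone, with a true change of 10 points and SD 16.7, false support is more likely than not up to about 12 crossovers (8 to 16 across the correlation range). Beyond that it becomes the less likely result. Every figure rests on an assumed crossover count, a back-solved SD that may not suit self-selected subjects, and an assumed correlation.

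A reader might also infer that the trial's main conclusion is at risk. It is not: Aim 4 is a non-randomised look at crossovers, and the between-arm comparison does not depend on it. This is a minor point on a secondary aim.

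**What to change.** Add an Aim 4 paragraph to Section V stating, for 4.2:

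- The result for each measure is the paired mean change from baseline to crossover with its 95% CI. Non-significance alone is not taken as support for no change.
- For the mHHS, conclude no important change only if the 95% CI lies wholly within a pre-specified margin. An example is ±10 points, borrowed from the Aim 1 power text, or another margin that the sponsor justifies.
- If that CI lies within the margin but excludes zero, report a change smaller than the margin.
- If the CI extends beyond the margin and excludes zero, report a change.
- If the CI extends beyond the margin and includes zero, report the result as inconclusive.
- The other instruments are reported descriptively with CIs, without margins.
- Time on PT before crossover is tabulated where recorded.

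The cost is one paragraph, with no effect on enrolment, randomisation or the primary analysis. Two practical limits remain. Surveys are tied to clinic visits, so the paragraph should say which survey counts as the crossover score. The therapist's sheet dates advancement or re-referral, but no stop date is specified for subjects who end PT themselves. The main downside is that with few crossovers the mHHS result will usually be inconclusive, which is what such data can support.
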